# **Secondary Objectives**

- 1. To assess the safety and tolerability of vemurafenib in patients with HCL
- 2. To assess the efficacy of vemurafenib based on time to response, duration of response, and kinetics of minimal residual disease (MRD) response assessed by immunohistochemistry
- 3. To determine the progression-free and overall survival of HCL patients treated with vemurafenib
- 4. To characterize molecular profiling of HCL by high throughput next generation sequencing using Raindance multiplex PCR and Ilumina next generation sequencing
- 5. To assess the pharmacodynamics of vemurafenib via measurement of BRAF downstream targets (MEK, p-MEK, ERK, p-ERK) from the peripheral blood or bone marrow aspirate samples, and by examining the MAPK, PI3K and JAK-STAT signaling pathways using Cell Biosciences NanoPro 1000 technology
- 6. To evaluate biomarkers that may be relevant to explain primary or acquired resistance to vemurafenib as assessed by additional BRAF mutations, reactivation of MAPK pathways, activation of alternative signaling pathways (e.g. PI3K and STAT)

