# 11.0 TOXICITIES/SIDE EFFECTS

# 11.1 Expected Side Effects of Vemurafenib

Although vemurafenib has been extensively studied in patients with melanoma in phase I, II and III trials, the side effects in patients with HCL are unknown. Based on clinical experience in patients with melanoma, following adverse events can be expected at the dose of 960mg b.i.d. Guidelines for management of the toxicity are given in Section 9.2.

- Common: rash, photosensitivity, pruritus, palmar-plantar erythrodysesthesia (PPE), cutaneous SCC, fatigue, arthralgia, dry skin, mild hair loss and acute kidney injury
- Uncommon: increased AST, ALT, alkaline phosphatase and bilirubin, fever, nausea, vomiting, diarrhea, anorexia, weight loss, headache, neuropathy, altered taste
- Rare: pancytopenia, pancreatitis, conjunctivitis, pericarditis, renal impairment, dysphagia, arthritis, gastrointestinal polyps, allergic reactions, Stevens-Johnson syndrome, drug reaction with eosinophilia and systemic symptoms (DRESS), retinal vein occlusion, Dupuytren's contracture and plantar fibromatosis, Peripheral Edema.

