#### 11.2 Assessments of Adverse Events

# 11.2.1 Adverse Events

An adverse event (AE) is any unfavorable and unintended sign, symptom, or disease temporarily associated with the use of an investigational medicinal product or other protocol-imposed intervention, regardless of attribution.

This includes the following:

- AEs not previously observed in the subject that emerge during the protocol-specified AE reporting period, including signs or symptoms associated with HCL that were not present prior to the AE reporting period.
- Complications that occur as a result of protocol-mandated interventions
- If applicable, AEs that occur prior to assignment of study treatment associated with medication washout, no treatment run-in, or other protocol-mandated intervention.
- Preexisting medical conditions (other than the condition being studied) judged by the investigator to have worsened in severity or frequency or changed in character during the protocol-specified AE reporting period.

To ensure consistency of AE and SAE (see below in Section 11.2.2) causality assignments, the following general guidelines should be applied:

- Yes: There is a plausible temporal relationship between the onset of the AE and administration of vemurafenib and the AE cannot be readily explained by the subject's clinical state, intercurrent illness, or concomitant therapies; and/or the AE follows a known pattern of response to vemurafenib; and/or the AE abates or resolves upon discontinuation of vemurafenib or dose reduction and, if applicable, reappears upon re-challenge.
- No: Evidence exists that the AE has an etiology other than vemurafenib (e.g., preexisting
  medical condition, underlying disease, intercurrent illness, or concomitant medication); and/or
  the AE has no plausible temporal relationship to vemurafenib administration (e.g., cancer
  diagnosed 2 days after first dose of study drug).

Expected AEs are those adverse events that are listed or characterized in the Package Insert (P.I.) or current Investigator Brochure (I.B.). Unexpected AEs are those not listed in the P.I. or current I.B. or not identified. This includes AEs for which the specificity of severity is not consistent with the description in the P.I. or I.B. For example, under this definition, hepatic necrosis would be unexpected if the P.I. or I.B. only referred to elevated hepatic enzymes or hepatitis.

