Toxicity will be graded and recorded using the NCI Common Toxicology Criteria version 4.0. Clinically significant adverse events will be noted and compared to the baseline condition. Adverse events that will be noted will include expected side effects, and any other clinically significant symptom or laboratory value. An assessment will be made concerning the severity of the event, and if the event appears to be related to the study drug. Adverse events, toxicity grading, and attributions will be recorded in the electronic database by the Clinical Research Associate (CRA) after review of the data by the Principal Investigator.

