# 11.2.3 Adverse Event Reporting Period

The study period during which all AEs and SAEs must be reported begins after informed consent is obtained and initiation of study treatment and ends 28 days following the last administration of study treatment or study discontinuation/termination, whichever is earlier. After this period, investigators should only report SAEs that are attributed to prior study treatment.

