# 17.2.2 SAE Reporting to Genentech (MSKCC STAFF ONLY)

MSK will be responsible for collecting all protocol-defined Adverse Events (AEs)/Serious Adverse Events (SAEs), pregnancy reports (including pregnancy occurring in the partner of a male study subject), other Special Situation reports, AESIs and Product Complaints with an AE where the patient has been exposed to Vemurafenib. The completed MedWatch form should be sent to the Genentech contact specified below.

[contact]

Email: usds\[contact]

All Product Complaints without an AE should call via:

PC [contact] (M-F: 5 am to 5 pm PST)

Transmission of these reports (initial and follow-up) will be either electronically via email or by fax and within the timelines specified below:

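### Section 11.2.1 ties the adverse events noted to clinical significance, while the AE definition and Sections 11.2.3 and 17.2.2 take in all of them, so the safety dataset depends on which rule was followed

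*Combined protocol and SAP*

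**What the plan says.** Section 11.2.1 opens by defining an adverse event as "any unfavorable and unintended sign, symptom, or disease temporarily associated with the use of an investigational medicinal product" or of another protocol-imposed intervention, whatever the attribution. The definition contains no significance threshold.

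The closing paragraph of the same section then describes what is noted. It says first: "Clinically significant adverse events will be noted and compared to the baseline condition". It goes on: "Adverse events that will be noted will include expected side effects, and any other clinically significant symptom or laboratory value". The paragraph ends with entry into the electronic database by the clinical research associate after principal investigator review.

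Section 11.2.3 sets the reporting window without a filter: "The study period during which all AEs and SAEs must be reported begins after informed consent is obtained and initiation of study treatment". Section 17.2.2 adds: "MSK will be responsible for collecting all protocol-defined Adverse Events (AEs)/Serious Adverse Events (SAEs".

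On the expected list, Section 11.1 says that "the side effects in patients with HCL are unknown" and takes its entries from experience in melanoma. Section 11.2.1 also defines expected events by the package insert or the current investigator brochure. The first secondary objective is "To assess the safety and tolerability of vemurafenib in patients with HCL", and Section 14.0 analyses it by tabulating safety data over all subjects.

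**The concern.** One section tells sites to note clinically significant events. Others tell them that every event meeting the definition must be reported and collected. A mild symptom that is on no list and that the investigator considers unimportant is reportable under the second instruction, but need not be noted under the first. The term clinically significant is not defined, and the documents do not say how it should be judged or which instruction prevails.

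The sentence on what is noted attaches the qualifier to symptoms and laboratory values other than the expected ones. Read that way, discretion falls mainly on unlisted events, in a disease where the protocol itself says the side effects are not known. Those events carry most of the new information for the safety objective. Non-serious, lower-grade events also bear on tolerability, because the drug is taken orally every day in 28-day cycles.

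**Working it through.** The plan states no figure on this point, so the check is mainly a comparison of text.

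**1. The rules applied to one event.** Take a grade 1 or 2 symptom that is non-serious, not an AE of special interest, not expected, and judged not clinically significant.

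- Definition in Section 11.2.1: it is an AE.
- Section 11.2.3: it must be reported if it occurs within the window.
- Section 17.2.2: it must be collected, since it is protocol-defined.
- Closing paragraph of Section 11.2.1: it falls outside both sentences on what is noted.

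The event is in the dataset under three texts and can be left out under the fourth.

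**2. Whether other text settles it.** Section 11.2.4 covers eliciting, recording and reporting. It asks for a consistent method and non-directive questions, and its severity scale includes a grade 1 for mild or asymptomatic findings. It has no significance filter, but it neither refers to the filter in Section 11.2.1 nor overrides it. The two sections also name different versions of the toxicity criteria (4.0 in 11.2.1, 5.0 in 11.2.4), so they were not aligned in other respects either.

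**3. What is exposed.** Section 11.2.2 gives serious events their own route. A note to the severity scale in Section 11.2.4 sends grade 4 and 5 events through serious-event reporting. The same section lists AEs of special interest, among them acute kidney injury, bone marrow toxicity, liver injury and QT prolongation. What remains is non-serious, lower-grade events outside that list.

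**4. Illustration of size.** Inputs: N = 36 (Section 14.0). Assumed, with no source in the documents: p, the true per-patient rate of an unlisted event, and c, the share of cases judged clinically significant and so recorded, taken as independent across patients.

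Expected recorded cases = N × p × c. Chance of recording at least one = 1 − (1 − p × c)^36.

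| p | c | Expected cases | Chance of at least one |
|---|---|---|---|
| 10% | 1 | 3.6 | 97.7% |
| 10% | 0.75 | 2.7 | 94.0% |
| 10% | 0.5 | 1.8 | 84.2% |
| 10% | 0.25 | 0.9 | 59.8% |
| 5% | 1 | 1.8 | 84.2% |
| 5% | 0.75 | 1.35 | 74.7% |
| 5% | 0.5 | 0.9 | 59.8% |
| 5% | 0.25 | 0.45 | 36.4% |

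The rows with c = 1 correspond to recording every event. The other rows show only how the result moves with the assumed c.

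**The case against.** The strongest reply is that the paragraph can be read more mildly.

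- Its verb is inclusive and does not say that nothing else is noted. This stands as a matter of wording. But if everything were noted anyway, the qualifier on other symptoms and laboratory values would do no work, so a site could reasonably take it as a limit.
- The preceding sentence applies clinical significance to adverse events in general. Expected events might then be filtered too. This also stands: it makes the tilt towards unlisted events less certain, while widening the conflict with Section 11.2.3.
- Section 11.2.4 looks like the working procedure and has no filter. That supports full recording as the intention, but does not remove the contrary sentences.
- Monthly all-site teleconferences (Section 16.1) and principal investigator review before entry may even out practice between sites. Neither supplies a definition of significance.
- Accrual closed in August 2016, so new wording cannot recover events that were not recorded. This stands. However, Table 3 still schedules AE review during re-treatment, and the safety table has to be interpreted.

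A reader might go further and infer that new events have been under-counted, or that the safety profile will resemble melanoma by construction. The documents do not support that. They do not show which rule sites followed, the qualifier may apply to expected events as well, and the expected set also depends on the package insert and brochure, whose contents are not given.

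**Conclusion.** The inconsistency is in current text and nothing in the documents resolves it. Following the closing paragraph of Section 11.2.1 in good faith can give a smaller AE dataset than following the definition with Sections 11.2.3 and 17.2.2. Non-serious, lower-grade events are the ones exposed, mainly unlisted ones if the second sentence is given its natural reading.

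The size of any under-count cannot be derived from the documents. The tabulated figures rest on assumed event rates and assumed shares judged significant, and show sensitivity only. The effect is confined to a descriptive secondary safety tabulation. The primary response endpoint and the two-stage decision rule are not touched. The wording should be corrected, and the rule actually used should be disclosed with the results.

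**What to change.** In Section 11.2.1, replace the two sentences that refer to clinical significance with one rule: all AEs as defined in that section are recorded, of any grade, expected or not, regardless of attribution or clinical significance. Comparison with the baseline condition can be kept. Make the wording consistent with Sections 11.2.3 and 17.2.2.

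Do not add a separate grade 3 threshold for laboratory values. It would contradict recording at any grade, and could lose grade 1-2 liver or creatinine changes that the present text captures as expected effects or as clinically significant values.

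For data already collected, state alongside the AE table which rule was followed, by site if practice differed.

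The cost is a short text change, one reporting statement, and more low-grade entries at the sites. It will not restore events already left out.

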#### 11.2.2 Serious Adverse Events (SAEs) Reporting

An adverse event is considered serious if it results in ANY of the following outcomes:

- Death
- A life-threatening adverse event
- An adverse event that results in inpatient hospitalization or prolongation of existing hospitalization
- A persistent or significant incapacity or substantial disruption of the ability to conduct normal life functions
- A congenital anomaly/birth defect
- Important Medical Events (IME) that may not result in death, be life threatening, or require hospitalization may be considered serious when, based upon medical judgment, they may jeopardize the patient or subject and may require medical or surgical intervention to prevent one of the outcomes listed in this definition

Note: Hospital admission for a planned procedure/disease treatment is not considered an SAE. SAE reporting is required as soon as the participant starts investigational treatment/intervention. SAE reporting is required for 30-days after the participant's last investigational treatment/intervention. Any event that occur after the 30-day period that is unexpected and at least possibly related to protocol treatment must be reported.

Please note: Any SAE that occurs prior to the start of investigational treatment/intervention and is related to a screening test or procedure (i.e., a screening biopsy) must be reported.

All SAEs must be submitted in PIMS. If an SAE requires submission to the HRPP office per IRB SOP RR-408 'Reporting of Serious Adverse Events', the SAE report must be submitted within 5 calendar days of the event. All other SAEs must be submitted within 30 calendar days of the event.

The report should contain the following information:

- The date the adverse event occurred
- The adverse event
- The grade of the event
- Relationship of the adverse event to the treatment(s)
- If the AE was expected
- Detailed text that includes the following

- o An explanation of how the AE was handled
- A description of the participant's condition
- Indication if the participant remains on the study
- If an amendment will need to be made to the protocol and/or consent form
- If the SAE is an Unanticipated Problem

#### For IND/IDE protocols:

The SAE report should be completed as per above instructions. If appropriate, the report will be forwarded to the FDA by the IND Office

# 11.2.3 Adverse Event Reporting Period

The study period during which all AEs and SAEs must be reported begins after informed consent is obtained and initiation of study treatment and ends 28 days following the last administration of study treatment or study discontinuation/termination, whichever is earlier. After this period, investigators should only report SAEs that are attributed to prior study treatment.

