# g. AEs of Special Interest (AESIs)

AESIs are a subset of Events to Monitor (EtMs) of scientific and medical concern specific to the product, for which ongoing monitoring and rapid communication by the Investigator to the Sponsor is required. Such an event might require further investigation in order to characterize and understand it. Depending on the nature of the event, rapid communication by the trial Sponsor to other parties (e.g., Regulatory Authorities) may also be warranted.

Adverse events of special interest for this study include the following:

- Cases of potential drug-induced liver injury that include an elevated ALT or AST in combination with either an elevated bilirubin or clinical jaundice, as defined by Hy's law: Treatment-emergent ALT or AST > 3 × ULN in combination with total bilirubin > 2 × LILN
  - Treatment-emergent ALT or AST > 3 × ULN in combination with clinical jaundice
- Data related to a suspected transmission of an infectious agent by the study drug (STIAMP), as defined below:
  - Any organism, virus, or infectious particle (e.g., prion protein transmitting transmissible spongiform encephalopathy), pathogenic or non-pathogenic, is considered an infectious agent. A transmission of an infectious agent may be suspected from clinical symptoms or laboratory findings that indicate an infection in a patient exposed to a medicinal product. This term applies only when a contamination of the study drug is suspected
- Acute Kidney Injury
- Bone Marrow Toxicity
- Cutaneous Squamous Cell Carcinomas
- Gastrointestinal Polyps
- Hypersensitivity and Severe Cutaneous Reactions
- Liver Injury
- New/Second Primary Melanomas
- Non cutaneous Squamous Cell Carcinomas
- Pancreatitis
- Photosensitivity
- Potentiation of Radiation Toxicity
- Progression of RAS Mutant Malignancies
- QT Prolongation
- Retinal Vein Occlusion
- Uveitis
- VII Nerve Paralysis

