# 11.8 Cutaneous Squamous Cell Carcinoma

Cutaneous squamous cell carcinoma (cuSCC) is defined as an AE of special interest. Investigator and patient should perform routine skin examination at least once per cycle (28 days). Suspicious lesions or rashes should be referred to a dermatologist. A dermatologist should perform a full skin exam during screening/baseline, after 4 weeks of treatment, and every 12 weeks thereafter until discontinuation of the drug. Patients who withdrew from the study for any reason will be followed for SCC evaluation for 6 months after study drug discontinuation, start of new antineoplastic therapy, or until death, withdrawal of consent, or lost to follow up, whichever occurs first. Additionally, at baseline, the dermatologist will perform a complete dermatological history of prior medications, non-melanoma skin cancers, including SCC and actinic keratosis and their associated treatments, and risk factors for development of cutaneous malignancies (e.g. radiation therapy, sun exposure, phototherapy, use of tanning beds, genetic conditions, and immunosuppression).

Any lesion at baseline or during treatment that is clinically suspected of representing a cuSCC, basal cell carcinoma, actinic keratosis, primary melanoma, or other skin condition identified by the dermatologist should be completely resected by a dermatologist and submitted for pathologic review. A dose reduction is not indicated for this adverse event.

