# 11.9 Non-Cutaneous Squamous Cell Carcinoma

- Head and neck examination: A thorough head and neck examination to monitor for noncutaneous SCC, consisting of at least visual inspection of the oral mucosa and lymph node palpation, will be performed by the treating physician during screening/baseline, after 4 weeks of treatment, and every 12 weeks thereafter until a maximum of 6 months after discontinuation of study drug or at the start of new antineoplastic therapy, death, withdrawal of consent, or lost to follow up whichever occurs first.
- Chest CT scans: A chest CT scan will be performed during screening/baseline (up to 28 days prior to start of treatment) and, if considered clinically indicated at the discretion of treating physicians, at Cycle 3 Day 28.

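### Section 11.2.3 narrows reporting to treatment-attributed SAEs from 28 days after the last dose, while SCC surveillance runs to 6 months, so a non-serious cutaneous SCC found in follow-up may not reach the safety data

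*Combined protocol and SAP*

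**What the plan says.** Surveillance after the drug:

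- Section 11.8, cutaneous SCC: "Patients who withdrew from the study for any reason will be followed for SCC evaluation for 6 months after study drug discontinuation", with earlier stopping for reasons such as new anticancer treatment or death. The same section names cutaneous SCC an AESI.
- Section 11.9, non-cutaneous SCC: head and neck examination "every 12 weeks thereafter until a maximum of 6 months after discontinuation of study drug".
- Table 2: an end-of-treatment visit at 4 weeks, then a visit every 3 months up to 12 months. Its rows include dermatology and head and neck examination. It has no Adverse Events row, whereas Tables 1 and 3 have one.

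Reporting after the drug:

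- Section 11.2.3: the period for all AEs and SAEs "ends 28 days following the last administration of study treatment or study discontinuation/termination, whichever is earlier". Then: "After this period, investigators should only report SAEs that are attributed to prior study treatment".
- Section 11.2.2, repeated in 17.2: "SAE reporting is required for 30-days after the participant's last investigational treatment/intervention". Then: "Any event that occur after the 30-day period that is unexpected and at least possibly related to protocol treatment must be reported".
- Section 11.2.4, Post-Study Adverse Events: SAEs attributed to vemurafenib stay reportable, with no time limit and no test of expectedness.
- Section 11.2.4, AESIs: "ongoing monitoring and rapid communication by the Investigator to the Sponsor is required". Section 17.2.2 sets 15 or 30 calendar days from awareness for sending AESIs on to the company. Neither place gives an end date or a seriousness test.

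Section 11.1 places cutaneous SCC among the common expected effects: "palmar-plantar erythrodysesthesia (PPE), cutaneous SCC, fatigue, arthralgia". Section 14.0 tabulates safety data over all patients without stating a time window.

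**The concern.** The issue is not the two-day difference between the 28- and 30-day windows. Neither window matches the period over which the protocol looks for SCC. A lesion found at the 3- or 6-month visit and removed without admission can be judged non-serious, and section 11.2.3 then leaves it outside what investigators report. No rule clearly carries such a finding from the follow-up examination into the AE data.

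Safety and tolerability is the first secondary objective, and cutaneous SCC is singled out as an event of special interest. With 36 patients, one unrecorded case moves the observed rate by 1/36 = 2.8 percentage points, and two by 2/36 = 5.6 points. If sites resolve the ambiguity differently, the reported rate partly reflects site practice.

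**Working it through.** The plan gives no figure to reproduce on this point. The check compares time windows and then follows one case through each rule.

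**Step 1: time outside the windows.** Take 6 months as 365.25/2 = 182.6 days (11.8, 11.9) and reporting windows of 28 days (11.2.3) and 30 days (11.2.2, 17.2).

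Share outside = (surveillance days − window days) / surveillance days

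- 28-day window: (182.6 − 28)/182.6 = 154.6/182.6 = 84.7%
- 30-day window: (182.6 − 30)/182.6 = 152.6/182.6 = 83.6%

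The 4-week end-of-treatment visit falls at the edge of the window. The 3- and 6-month visits both fall outside it. For a patient who leaves the study early, section 11.2.3 can close the window before day 28.

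**Step 2: a non-serious cutaneous SCC found at month 3.**

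| Rule | Condition after the window | Result |
|---|---|---|
| 11.2.3 | SAE and attributed to treatment; limited by the word only | Not to be reported |
| 11.2.4, Post-Study AEs | SAE and attributed | Not required |
| 11.2.2 and 17.2 | Unexpected and at least possibly related | Not required if expected; 11.1 lists it |
| 11.2.4 AESIs, 17.2.2 | AESI; no end date, no seriousness test | Could require it, but conflicts with 11.2.3 |

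**Step 3: the same SCC judged serious and attributed.** Sections 11.2.3 and 11.2.4 (Post-Study AEs) both keep it reportable, expected or not. Without admission or another listed outcome, seriousness turns on the medical-judgement clause for important medical events in 11.2.2. Capture therefore depends on a site decision.

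**Step 4: illustration of size.** The documents give no post-drug SCC risk. Assume, for illustration only, a 6-month risk q of 5%, 10% or 20% at constant hazard in 36 patients. Expected cases = 36q. Expected cases after day w = 36 × [(1 − q)^(w/182.6) − (1 − q)].

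| Assumed q | Expected cases in 6 months | After day 28 | After day 30 |
|---|---|---|---|
| 5% | 1.8 | 1.52 | 1.50 |
| 10% | 3.6 | 3.02 | 2.98 |
| 20% | 7.2 | 5.99 | 5.90 |

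These are cases arising after the window, not cases lost. The loss is limited to those that a site does not report under any of the rules in step 2.

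**The case against.** The strongest reply is the AESI route. Cutaneous SCC is a named AESI, the duty is described as ongoing, the forwarding times run from awareness, and section 17.2.2 lists AESIs for collection alongside AEs and SAEs. A reader might infer that AESI reporting simply lapses at day 28. The documents do not say that. Equally, nothing says that the AESI duty overrides section 11.2.3, which covers all AEs and then restricts reporting. What stands is an unresolved conflict, not an exclusion.

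Other parts of the reply also stand:

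- A reader might infer that expected events are shut out. Sections 11.2.2 and 17.2 set a minimum and forbid nothing. Expectedness formally rests on the package insert or investigator brochure (11.2.1), which were not available.
- A reader might extend the loss to non-cutaneous SCC, new primary melanoma and progression of RAS-mutant malignancy. Section 11.1 does not list these. If they are also absent from the package insert and brochure, section 11.2.2 requires them when possibly related.
- Recording is not shown to stop. Section 11.2.1 has expected side effects noted and entered in the database, section 11.2.4 asks for AEs to be elicited at every evaluation, and section 14.0 applies no cut-off. Loss from the safety table is possible, not demonstrated.
- Seriousness is open: the severity table in 11.2.4 sends any event assessed as a significant medical event to SAE reporting.
- Surveillance is less firm than it looks. Section 11.8 words its 6 months for patients who withdrew, and Table 2's dermatology row carries a clinically-indicated footnote.
- Accrual closed in August 2016 and this version is dated June 2022, so new wording mainly affects patients still being re-treated. Those patients have AE review again under Table 3.

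These points limit the size and certainty of the problem. They do not remove the restriction in section 11.2.3 or say which rule governs.

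**Conclusion.** The concern holds in limited form. About 84–85% of the 6-month SCC surveillance time lies beyond the reporting windows, and a non-serious cutaneous SCC found then need not be reported under section 11.2.3. The AESI provisions may capture it, but the protocol does not settle the conflict, so the cutaneous SCC rate can be biased low by an amount that the documents do not allow one to estimate.

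This rests on two assumptions: that some cutaneous SCCs will be judged non-serious, and, for sections 11.2.2 and 17.2 only, that the package insert or brochure treats cutaneous SCC as expected, as section 11.1 does. It would be wrong to conclude that 85% of cases are lost or that the rate is certainly biased: the percentage is calendar time, and no post-drug hazard or share of non-serious cases is given. The change is worth making because the trial deliberately looks for these events.

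**What to change.** State one rule in section 11.2.3: SCC AESIs and, for consistency, the other malignancy AESIs are recorded and sent to the sponsor through the end of the existing post-treatment follow-up, whatever their seriousness or expectedness. Align 11.2.2, 11.2.4 (AESIs and Post-Study Adverse Events), 17.2 and 17.2.2 with it. Add an AE/AESI row to Table 2. In section 14.0, include these events in the safety tabulation with time from last dose.

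For patients already past follow-up, recover cases from the follow-up dermatology and head and neck records before the final report.

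The cost is a wording amendment, a few extra forms at visits already scheduled, some record review, and possibly a slightly higher reported SCC rate. No treatment or examination schedule changes.
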